5.4 Study Rationale

AD is a common inflammatory skin disorder characterized by recurrent eczematous lesions and intense itch. It is a major non-communicable disease that affects both children and adults and is the leading cause of the global burden from skin disease (Langan et al, 2020). It is estimated that 1 in 10 individuals will develop eczema during their lifetime. Eczema impacts people of all skin colors, races, and ethnicities (range 10 to 13%) (National Eczema Association).

AD involves a complex interplay of inflammatory pathways with multiple cytokines and inflammatory and epithelial cells implicated, with AD lesions always associated with underlying immune activation. Alarmins, which include TSLP, are endogenous, constitutively expressed chemotactic and immune activating peptides that are released following degranulation, cell injury or upon immune induction (Yang et al, 2017). TSLP is an IL-7-like cytokine expressed by epithelial cells and keratinocytes, and a key instigator of the immune response to environmental insults, initiating a range of downstream inflammatory pathways (Gauvreau et al, 2020). A common symptom of pruritis observed in AD can be attributed to TSLP signalling indirectly via the aforementioned inflammatory cascade but also via direct activation by TSLP of a specific subset of sensory neurons expressing TSLPR and the ion-channel transient receptor potential ankyrin 1 (TRPA1), further validating the targeting of TSLP in AD therapies (Wilson et al 2013). BSI-045B is designed to inhibit TSLP binding to the TSLP receptor, thereby inhibiting the inflammatory cascade and direct activation by TSLP of a specific subset of sensory neurons expressing TSLPR and the ion-channel TRPA1 associated with atopic dermatitis.

Anti-TSLP therapy has been clinically validated and is an effective treatment for allergic inflammatory diseases such as severe asthma (Menzies-Gow et al, 2021) and has shown clinical activity in patients with moderate to severe atopic dermatitis (Parnes et al, 2019). In vitro studies with BSI-045B demonstrated that the IP inhibits the TSLP pathway and

V4.0_8 Jul 2024 Page 32 of 68

production of downstream cytokines. BSI-045B is an anti-TSLP mAb being investigated to treat moderate to severe AD.

In animal models, BSI-045B reduced levels of inflammatory factors and eosinophil production in a dose-dependent manner. In preclinical studies, BSI-045B was safe and well tolerated, and no treatment-related abnormal changes were observed during administration and recovery. BSI-045B is not associated with irritation at the injection site and has a low incidence of immunogenicity.

This study is a Phase 2a, multicenter, proof-of-concept clinical trial to evaluate efficacy and safety of BSI-045B mAb injection in patients with moderate to severe atopic dermatitis. The study will also evaluate the tolerability, PK, immunogenicity, and PD/biomarker of BSI-045B following SC injections. The findings from this proof-of-concept study will be used to design a follow-on Phase 2b study.

5.5 Proposed Strengths and Dose Justification

Good Laboratory Practice (GLP) toxicity studies conducted with BSI-045B in cynomolgus monkeys showed that the IP is well tolerated up to 600 mg/kg (more than 16-fold the human equivalent dose for the maximum single dose (720 mg) administered in the Phase 1 clinical study) when administered as a single dose by SC injection. Further evaluation of the toxicity of BSI-045B was performed through a GLP repeat dose study (TQC-TOX-01) in which 5 doses of BSI-045B were administered SC to cynomolgus monkeys with a 1-week interval between administrations, followed by a 4-week recovery period. Doses of 30, 100 and 300 mg/kg were administered, with the high dose administered giving a human equivalent dose 19.4-fold higher than the clinical dose (300 mg) to be administered in the Phase 2a clinical trial. As in the single-dose study, no relevant toxicity findings were observed that were attributable to BSI-045B and the no observed adverse effect level (NOAEL) was considered to be 300 mg/kg for repeat dose administration up to 5 cycles. No significant toxicity findings were observed following weekly SC administration of BSI-045B to cynomolgus monkeys at 15, 50, and 150 mg/kg for 26 consecutive weeks. The NOAEL of BSI-045B was considered to be 150 mg/kg over 26 consecutive weeks, with an HED of 2,903 mg for a 60-kg subject, resulting in a safety margin of 9.7-fold above the clinical dose (300 mg) to be administered in the Phase 2a clinical study.

Local tolerance assessment revealed no BSI-045B related abnormalities on clinical or microscopic evaluation of the injection site, and immunotoxicity evaluation revealed no noteworthy findings.

No sex-related effect in the toxicity of BSI-045B after SC administration was evident in the nonclinical studies performed in monkeys (BSI-045B Investigator's Brochure). Nonclinical pharmacology studies have demonstrated BSI-045B's efficacy in binding, in a highly specific manner, to human TSLP in vitro. BSI-045B was also shown to inhibit the ability of TSLP to bind to its target receptor in an in vitro cell based model, using TSLPR expressing HEK293 cells. (BSI-045B Investigator's Brochure). Like BSI-045B, tezepelumab is a monoclonal antibody that specifically binds to human TSLP and acts on the same target as BSI-045B.

V4.0_8 Jul 2024 Page 33 of 68

Parnes et al (2019) reported results from a Phase 1 study in which tezepelumab was administered as a single SC dose (2.1, 7, 21, 70, 210, or 420 mg) or an intravenous (IV) dose (210 or 700 mg) to healthy subjects and following SC injections in multiple dose regimens of 35, 105, 210 mg or IV injections of 700 mg over a 3-month period. Parnes also reported results from a single IV injection of 700 mg in AD patients. In addition, Parnes and Sakamoto et al (2020) conducted independent phase 1 PK studies and determined that tezepelumab followed a linear disposition over various SC dosing levels and dosing intervals (including Q7D) up to 3 months.

Parnes et al (2019) reported mean PK parameter values for C_{max} and AUC over the dosing interval following an IV dose of 700 mg of tezepelumab administered Q28D over 3 months. The reported C_{max} was 370 μ g/mL and the AUC was 4050 day* μ g/mL. Following a single highest SC dose of 420 mg, the mean C_{max} was 58 μ g/mL and AUC $_{inf}$ was 2140 day* μ g/mL or 51360 h* μ g/mL Parnes also reported no differences between HVs and AD patients in mean values of various PK parameters. Zheng et al (2021) reported that although PK parameter values were slightly lower following SC injection into the arm, and there were no clinically significant differences between arm, abdomen, and thigh injections following an SC vial and syringe injection of 210 mg tezepelumab.

Simpson et al (2018) reported results from a Phase 2a, randomized, double-blind, placebocontrolled study at 26 centers in Australia, Canada, Germany, Hungary, New Zealand, and the United States. The 12-week study evaluated the efficacy and safety of tezepelumab in patients with moderate to severe AD who were treated with continuous concomitant class 3 topical corticosteroids (TCS). The effects of tezepelumab in patient-reported outcomes and impact of serum biomarkers on treatment responses were also reported. Following SC injections of 280 mg of tezepelumab every 2 weeks plus TCS, patients with moderate to severe AD achieved numerical improvements over placebo in the percent achieving 50% improvement on the EASI at week 12; however, these improvements were not statistically significant. In a safety analysis of the as-treated population (N=111), TEAEs were mild or moderate in severity (grade 1-2) and no deaths were reported. The most frequent TEAE that was considered by the investigators to be possibly treatment related was injection site erythema, which was reported in 3 (5.4%) of patients receiving tezepelumab and none in the placebo group. Numerical improvements were seen across several clinical and patientreported endpoints, and greater efficacy in biomarker-defined subgroups suggested potential benefits in TSLP blockade. Simpson et al (2018) postulated that limitations of their study may have been confounded by the patient population selected (only 10% of patients had severe disease); patients were not required to be refractory to TCS at baseline, patients applied high-strength TCS during the 2-week run-in period, and the dose selected may not have provided a complete inhibition of TSLP. This study will investigate the safety, tolerability, PK, biomarkers, and impact of using higher SC doses of BSI-045B in AD patients than previously used with tezepelumab. Higher doses may increase receptor occupancy, leading to a more pronounced biomarker and clinical response. The study results will provide additional information that will be used to better design future studies investigating whether BSI-045B is associated with significant clinical effects.

V4.0_8 Jul 2024 Page 34 of 68

For Study BSI-045B-002, the proposed SC doses of 300 mg administered weekly (QW) for 3 doses (loading dose) or twice weekly (Q2W) (maintenance dose) fall within the dose range of SC administration of 240 mg and 480 mg previously evaluated in a Phase 1 MAD study.

The dosing intervals proposed for Study BSI-045B-002, including QW/Q2W, are designed to meet or exceed the weekly (Q7D) interval investigated in the Phase 1 MAD study. In that study, BSI-045B was observed by a mono-exponential reduction in concentration after reaching peak levels. According to the principle of superposition, which is generally applicable in such cases, the concentration levels following each dose are expected to be superimposed on the levels after the prior dose. With these proposed dosing intervals being equal to or longer than those in the MAD study, the peak concentrations of the drug in Study BSI-045B-002 are anticipated to be similar to or lower than those in the MAD study. This implies that, if peak drug concentration is a key factor in toxicity, the safety profile of the proposed dosing regimen in Study BSI-045B-002 should be comparable to, or more favorable than, what was observed in the Phase 1 MAD study. A detailed evaluation of the PK characterization from Study BSI-045B-001 is presented in Section 5.2.3.3.

5.6 Risks and Benefits of BSI-045B in Human Volunteers Patients with Atopic Dermatitis

Good Laboratory Practices (GLP) toxicity studies conducted with BSI-045B in cynomolgus monkeys showed that the drug is well tolerated up to 600 mg/kg (more than 16-fold the human equivalent dose (HED) for the maximum single dose (720 mg) administered in the Phase 1 clinical study) when administered as a single dose by SC injection. Further evaluation of BSI-045B's toxicity was performed through a GLP repeat dose study (TQC-TOX-01) in which 5 doses of BSI-045B were administered SC to cynomolgus monkeys with a 1-week interval between administrations, followed by a 4-week recovery period. Doses of 30, 100 and 300 mg/kg were administered, with the high dose administered giving an HED 19.4-fold higher than the clinical dose (300 mg) to be administered in the Phase 2a clinical trial. As in the single dose study, no relevant toxicity findings were observed that were attributable to BSI-045B and the NOAEL was considered to be 300 mg/kg for repeat dose administration up to 5 cycles. Additionally, a 26-week GLP toxicity study with an 8-week recovery period in sexually mature cynomolgus monkeys was conducted. Monkeys were dosed with BSI-045B SC at 0, 15, 50 or 150 mg/kg/week. No significant toxicity findings were observed following weekly SC administration of BSI-045B to cynomolgus monkeys at 15, 50, and 150 mg/kg for 26 consecutive weeks. The NOAEL of BSI-045B was considered to be 150 mg/kg over 26 consecutive weeks, with an HED of 2,903 mg for a 60-kg subject, resulting in a safety margin of 9.7-fold above the clinical dose (300 mg) to be administered in the Phase 2a clinical study.

Local tolerance assessment revealed no abnormalities attributable to BSI-045B on clinical or microscopic evaluation of the injection site, and immunotoxicity evaluation revealed no noteworthy findings.

Biosion Australia Pty Ltd is currently completing a Phase 1 study in Australia. The study consists of 3 parts: Part A, a SAD study in HVs; Part B, a single-dose study in patients with AD; and Part C, a MAD study in HVs. An interim analysis was conducted to analyze the

V4.0_8 Jul 2024 Page 35 of 68

safety and PK data. In the interim analysis, a total of 54 participants, including 28 (51.9%) men and 26 (48.1%) women, were assessed. The actual numbers of subjects in Part A Cohort 1 (120 mg), Cohort 2 (240 mg), Cohort 3 (480 mg), and Cohort 4 (720 mg) were 8, 8, 8, and 8; the actual number of patients in Part B was 5; the actual number of subjects in Part C Cohort 1 (240 mg Q7D) was 9, and Cohort 2 (480 mg Q7D) was 8.

According to the interim analysis for this Phase 1 study, there were no serious TEAEs, TEAEs leading to death, or any deaths in any part of the study. There was 1 (1; 12.5% of group) severe TEAE (transaminases increased), reported by a subject in the 240-mg dose level Cohort in Part A. One subject (1; 11.1% of group in Part C; 240-mg Q7D Cohort) was withdrawn from the study due to TEAEs (increased AST and increased ALT).

Overall, the frequency of TEAEs was similar across all single and multiple dose levels, with most or all subjects in each cohort in Part A (SAD) and Part C (MAD) reporting at least 1 TEAE. In Part A, the frequency of study drug related TEAEs increased with dose level, indicating a potential relationship. In Part C, there was no increase in the frequency of study drug related TEAEs increasing with dose level. The frequency of TEAEs in Part B (patients with AD; 2 [40.4%]) was lower than the frequency of TEAEs at the same dose level in healthy volunteers in Part A (480 mg; 7 [87.5%]).

Treatment-emergent AEs in SOC General Disorders and Administration Site Conditions, most or all of which were injection site reactions, were the most common TEAEs by SOC in both Part A and Part C. A relationship between increasing dose level and the events injection site erythema and injection site pain was observed in Part A, and a relationship between increasing dose level and injection site swelling was observed in Part C. In Part B, no TEAE by Preferred Term was reported by greater than 1 (20.0%) of subjects. Except for the severe TEAE in Part A, all TEAEs in the study were mild or moderate.

Overall, injection site reactions were common in Part A and Part C of the study, although variances in the frequency and nature of reactions across dose levels were observed. Remarkably, in Part B no patients with AD reported injection site reactions on the day of study drug administration; 1 subject (20.0%) reported an injection site reaction (mild tenderness) on Day 2. Based on the clinical safety information of similar targeted drugs, injection site reactions are common adverse reactions, which could be regarded as potential risks for receiving BSI-045B treatment (Adbry® prescribing information, 2022).

Another Phase 1 study was conducted by an independent licensee (CTTQ) for BSI-045B (named as TQC2731 by CTTQ) in healthy adults to evaluate the safety, tolerability, PK, and immunogenicity of TQC2731. As listed in the study abstract submitted to the American Academy of Allergy Asthma and Immunology meeting 2023, 54 participants were enrolled. TQC2731/placebo-related AEs were mild or moderate in severity across all dosing groups. The incidence of AEs observed was not dose dependent. No drug-related SAEs were reported. In summary, TQC2731 was safe and well-tolerated (Liu et al, 2023).

Thus, based on both nonclinical and clinical data obtained with BSI-045B, this new monoclonal antibody is expected to be well tolerated in the proposed Phase 2a study. Up to

V4.0_8 Jul 2024 Page 36 of 68

this amendment to the study protocol, no specific safety signals have been observed in this study, indicating a safety profile of 300 mg monotherapy in AD patients.

V4.0_8 Jul 2024 Page 37 of 68

6 STUDY OBJECTIVES AND ENDPOINTS

Table 5. Objectives and Endpoints in BSI-045B-002 Study

Objectives	Endpoints	
Primary		
Primary Efficacy Objective:	Primary Efficacy Endpoint:	
To evaluate the efficacy of BSI-045B in patients with moderate to severe atopic dermatitis (AD)	Proportion of patients with ≥Eczema Area and Severity Index (EASI)75 at Week 26 (2 weeks after last dose at Week 24)	
Primary Safety Objective:	Primary Safety Endpoint:	
To evaluate the safety and tolerability of BSI-045B in patients with moderate to severe AD	Safety and tolerability as evidenced by the incidence of adverse events (AEs), anti-BSI-045B antidrug antibody (ADA) formation, clinical laboratory evaluations, 12-lead electrocardiography (ECGs), vital signs, and physical examinations. The relationships between study drugs and AEs will be evaluated by the Investigators.	
Secondary		
To evaluate the pharmacokinetics (PK) of BSI-045B	Pharmacokinetics listings will be provided. PK parameters might be estimated through compartmental modeling. Additionally, the PK/Efficacy relationship might be explored.	
To evaluate the immunogenicity of BSI-045B	Anti-BSI-045B ADA during and post BSI-045B treatment	
Exploratory		
To assess additional efficacy and safety outcomes of BSI- 045B	Proportion of patients with EASI90 at Week 26 (2 weeks after last dose at Week 24)	
	 Proportion of patients with EASI50 at Week 26 (2 weeks after last dose at Week 24) 	
	➤ Percent change from baseline in EASI at each visit	
	➤ Proportion of patients achieving Investigator's Global Assessment (IGA) 0 or 1 at 26 (2 weeks after last dose at Week 24)	
	 Percent changes in PP-NRS scores at Week 26 (2 weeks after last dose at Week 24) 	
	 Proportion of patients achieving Facial IGA 0/1 at Week 26 (2 weeks after last dose at Week 24) 	
	> Occurrence of conjunctivitis	

V4.0_8 Jul 2024 Page 38 of 68

Objectives	Endpoints
To evaluate the PD biomarkers of BSI-045B	Serum levels of thymus and activation regulated chemokine/C-C chemokine ligand 17 (TARC/CCL-17), periostin, and IgE during and post BSI-045B treatment

AD = atopic dermatitis; ADA = antidrug antibody; AE = adverse event; CCL-17 = C-C chemokine ligand 17; EASI = Eczema Area and Severity Index; ECG = electrocardiography; IGA = Investigator's Global Assessment; IgE = immunoglobulin E; ; PD = pharmacodynamic; PK = pharmacokinetic; PP-NRS = Peak Pruritus Numerical Rating Scale; TARC = thymus and activation regulated chemokine

V4.0_8 Jul 2024 Page 39 of 68

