7.9.3 Efficacy

Patients will be assessed to determine an EASI score at Screening, prior to dosing on Day 1 (baseline), at subsequent visits, and at the time of early withdrawal from the study.

The EASI score is a composite index that measures the severity of AD based on the average intensity of four clinical signs (erythema, edema/papulation, excoriations, and lichenification) at four body areas (head, neck, upper extremities, and trunk and lower extremities), and the percentage of affected area for each of the four body areas (Hanifin and Rajka, 1980). The primary efficacy endpoint is the proportion of patients with ≥EASI75 at Week 26 (2 weeks after last dose at Week 24).

The IGA and facial IGA require the Investigator to rate the severity of AD on a scale from 0 (clear) to 4 (severe).

The assessment tool for itching is the PP-NRS, on which the patient rates the maximum severity of the itch from AD on a scale from 0 (no itch) to 10 (worst itch imaginable) over a

V4.0_8 Jul 2024 Page 43 of 68

24-hour period. The baseline PP-NRS score is based on the average of daily PP-NRS scores for the 7 days immediately preceding Day 1. Patients will complete the rating scale daily using the patient diary beginning on Day -8, throughout the last study visit, and at the time of early withdrawal from the study. In order to calculate an average for the score, the patient must have completed the diary for a minimum of 4 days during the previous 7 days.

Exploratory efficacy and safety assessments will include the following. At each visit, the percentage of patients who achieve 50%, 75%, and 90% improvement in the EASI score from Day 1) and the change in EASI score from Day 1 will be calculated. Detailed analysis of all exploratory endpoint is described in the Statistical Analysis Plan (SAP).

- Proportion of patients with EASI90 at Week 26 (2 weeks after last dose at Week 24)
- Proportion of patients with EASI50 at Week 26 (2 weeks after last dose at Week 24)
- Percent change from baseline in EASI at each visit
- Proportion of patients achieving IGA 0 or 1 Week 26 (2 weeks after last dose at Week 24)
- Percent changes in PP-NRS scores at Week 26 (2 weeks after last dose at Week 24)
- Proportion of patients achieving Facial IGA 0/1 at Week 26 (2 weeks after last dose at Week 24)
- Occurrence of conjunctivitis

7.9.4 *Safety*

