8 STUDY POPULATION

8.1 Inclusion Criteria

Patients must meet the following criteria for study entry:

- 1) In the opinion of the Investigator, the patient is capable of understanding and complying with protocol requirements.
- 2) The patient signs and dates a written ICF prior to the initiation of any study procedures.
- 3) The patient has a diagnosis of AD (according to the criteria established by Hanifin and Rajka, 1980). The diagnosis of AD must have been present for at least 6 months.
- 4) The patient is aged 18 to 65 years, inclusive at the time of consent. Patients of any gender are eligible.
- 5) A female patient weighs at least 45 kg and a male patient weighs at least 50 kg. The patient has a BMI between 18.0 and 32.0 kg/m² inclusive at Screening.
- 6) The EASI is \geq 12 at Screening and on Day 1.
- 7) The score on the IGA is ≥ 3 (scale of 0 to 4) at Screening and on Day 1.
- 8) The total body surface area (BSA) affected by AD is $\geq 10\%$ as assessed by the physical examination at Screening and on Day 1.
- 9) The patient has:
 - (a) not received prior treatment with topical or systemic medications OR
 - (b) the patient has active disease despite topical or systemic treatment as per the Investigator at the time of screening.
 - Prescription moisturizers or moisturizers containing additives such as ceramide, hyaluronic acid, urea, or filaggrin degradation products can be allowed if the patient agrees to continue using at the current dose during the study.
- 10) A male patient who is non-sterilized and sexually active with a female partner of childbearing potential agrees to use highly effective contraception from the time of signing the ICF throughout the duration of the study treatment and for 90 days (~5 half-lives) after the last dose of study drug (See Section 8.3).
- 11) A female patient of childbearing potential who is sexually active with a non-sterilized male partner agrees to use highly effective contraception from the time of signing the ICF throughout the duration of the study treatment and for 90 days after the last dose of study drug (See Section 8.3).
- 12) The patient has a negative urine/blood result for drugs of abuse (if there are concerns in the opinion of the Investigators regarding the use of illicit drugs, including cannabinoid products).

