# 4.1.2 Baseline Definition and Change from Baseline and Percent Change from Baseline

Baseline data are defined as last non-missing assessment which are collected prior to or on the day of first dose, and must be prior to the administration of first dose, including scheduled and unscheduled visits, unless otherwise specified. Hence, change from baseline = post-baseline value – baseline value. Percent change from baseline = (post-baseline value – baseline value)/ baseline value×100%.

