# 4.7.3 Peak Pruritus Numerical Rating Scale (PP-NRS)

The assessment tool for itching is the PP-NRS, on which the subject rates the maximum severity of the itch from AD on a scale from 0 (no itch) to 10 (worst itch imaginable) over a 24-hour period. The baseline PP-NRS score is based on the average of daily PP-

NRS scores for the 7 days immediately preceding Day 1. In order to calculate an average for the score, the subject must have completed the diary for a minimum of 4 days during the previous 7 days.

Measured values, changes from baseline and percent change from baseline in PP-NRS score will be summarized descriptively at 2 weeks after last dose at Week 24.

The PP-NRS score at Week 26 (2 weeks after last dose at Week 24) is based on the average of the first consecutively 7 days recorded on visit of FU2, as the PP-NRS score for a treatment cycle will be collected at the next visit.

Mean (±standard deviation) of percent change from baseline of PP-NRS score with observed data will be plotted at scheduled visit.

A listing of all PP-NRS score will be provided by subject number.

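### The only by-visit itch display is mean ± SD of percent change in PP-NRS, but entry sets no minimum itch score, so one low-baseline patient who worsens can distort it and a zero baseline has no value.

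*Protocol*

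**What the plan says.** - **Endpoint.** Protocol section 6 (Table 5), repeated in SAP Table 1, gives one PP-NRS endpoint, under the exploratory objectives: "Percent changes in PP-NRS scores at Week 26 (2 weeks after last dose at Week 24").
- **Formula.** SAP 4.1.2: "Percent change from baseline = (post-baseline value – baseline value)/ baseline value×100"%.
- **Scale and baseline.** Protocol 7.9.3 has itch rated "on a scale from 0 (no itch) to 10 (worst itch imaginable"). It then says: "The baseline PP-NRS score is based on the average of daily PP-NRS scores for the 7 days immediately preceding Day 1". For an average to count, "the patient must have completed the diary for a minimum of 4 days during the previous 7 days".
- **Entry.** Protocol 8.1 sets Day 1 severity floors for EASI (at least 12), affected BSA (at least 10%) and IGA: "The score on the IGA is ≥ 3 (scale of 0 to 4) at Screening and on Day 1". None of the 12 inclusion or 26 exclusion criteria sets a floor for PP-NRS.
- **Outputs.** SAP 4.7.3 summarizes measured values, absolute change and percent change at Week 26, and lists all scores. By visit it plans one figure only: the mean ± SD "of percent change from baseline of PP-NRS score with observed data will be plotted at scheduled visit". SAP 4.1.1 gives n, mean, median, SD, minimum and maximum for continuous variables.
- **Zero or low baseline.** Neither document has a rule. SAP 4.1.5 leaves missing data as missing, without special handling, unless otherwise specified.

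**The concern.** Percent change is well behaved when the denominator is kept away from zero. The entry floor of 12 does that for EASI; nothing does it for PP-NRS, so a 7-day average of 0, or of a fraction of a point, is an admissible baseline.

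Two things follow. At a baseline of 0 the endpoint cannot be computed, and the plan does not say what happens to that patient. At a low baseline the measure is lopsided: improvement stops at -100%, while a worsening of 1 or 2 points can be +100% to +300%. With 20 to 24 patients, one such value can carry the mean and inflate the SD, and those are the two quantities plotted by visit. Protocol 5.4 uses a direct effect of TSLP on itch-sensing neurons as part of its rationale and says the findings will feed the Phase 2b design, so the itch curve will be looked at.

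**Working it through.** **The plan's own figure.** The documents give no precision or distribution for PP-NRS. Their only sample-size figures, the one-sided exact widths of 21% and 19% for EASI75, reproduce (20.8% at n=20, 18.8% at n=24) but have no bearing here.

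**Inputs.** n = 20 to 24 (Protocol 7.1); scale 0 to 10 (Protocol 7.9.3); the percent-change formula of SAP 4.1.2. Assumption for illustration: every other patient goes from 7 to 3.5, which is -50% and -3.5 points.

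**1. One patient going from 1 to 3.** Percent change = (3 - 1)/1 × 100 = +200%.
- Mean percent change, n=20: (19 × (-50) + 200)/20 = -37.5%.
- Mean percent change, n=24: (23 × (-50) + 200)/24 = -39.6%.
- Mean absolute change, n=20: (19 × (-3.5) + 2)/20 = -3.23 points.
- Mean absolute change, n=24: (23 × (-3.5) + 2)/24 = -3.27 points.

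**2. One patient going from 0.5 to 2 (+300%).** Mean percent change = (19 × (-50) + 300)/20 = -32.5% (n=20), or (23 × (-50) + 300)/24 = -35.4% (n=24).

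**3. The same kind of patient improving instead.** The most that can happen is -100%: (19 × (-50) - 100)/20 = -52.5%, a shift of 2.5 points at n=20. The distortion therefore needs both a low baseline and a rise in itch.

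**4. Median and SD, by simulation.** 20,000 runs; assumed baselines uniform on 4 to 10, proportional reduction with mean 50% and SD 30%, follow-up kept within 0 to 10. Values are averages over runs.

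| | Mean % | Median % | SD of % | Mean absolute change |
|---|---|---|---|---|
| n=20, no low-baseline patient | -49.5 | -50.0 | 28.2 | -3.46 |
| n=20, one patient 1 to 3 | -37.1 | -48.1 | 62.3 | -3.20 |
| n=24, no low-baseline patient | -49.5 | -50.0 | 28.3 | -3.47 |
| n=24, one patient 1 to 3 | -39.1 | -48.4 | 58.1 | -3.24 |

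One patient roughly doubles the SD and moves the mean by 10 to 12 points. The median moves by less than 2 points, and the mean absolute change by less than 0.3 of a point.

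**5. How often a baseline below 1 would occur.** Assume baseline PP-NRS is normal, truncated to 0 to 10. With p the chance that one patient is below 1, the chance of at least one such patient is 1 - (1 - p)^n.
- Mean 7, SD 2: p = (Φ(-3) - Φ(-3.5))/(Φ(1.5) - Φ(-3.5)) = 0.0012, giving 2.4% (n=20) to 2.8% (n=24).
- Mean 6, SD 2.5: p = (Φ(-2) - Φ(-2.4))/(Φ(1.6) - Φ(-2.4)) = 0.0155, giving 27% (n=20) to 31% (n=24).

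These are chances of the low baseline alone, so they are upper bounds on the chance that such a patient also worsens.

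**6. Zero baseline.** The formula divides by 0, so there is no percent change at any visit. Absolute change remains defined, but SAP 4.7.3 tabulates it at Week 26 only.

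**The case against.** The best defence is that little rests on this summary. The endpoint is exploratory, SAP 4.1.1 plans no hypothesis tests, and the sample size concerns EASI75 alone. The SAP already plans most of the protection: at Week 26 the table will carry absolute change and the median, minimum and maximum of percent change, so a +200% maximum beside a median near -50% would be plain to see. A zero-baseline patient would show as a smaller n and would still count in absolute change at Week 26. Entry floors on EASI, IGA and BSA also make near-zero itch less likely. All of this stands, and it keeps the point minor. It does not cover the by-visit plot, which shows only the mean and SD of percent change, or the absence of a zero-baseline rule.

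Three stronger readings are tempting, and the documents do not support them.
- **That a distorting patient is likely.** Under the same assumed distributions, the chance of at least one baseline below 2 is 12-14% to 64-71%. But the large shifts above come from baselines of 0.5 to 1, and they also need worsening. Neither document gives data on either event.
- **That the endpoint must become absolute change.** Absolute change depends on baseline too: a patient starting at 1 can improve by at most 1 point. Redefining a protocol endpoint would need an amendment with IRB approval (Protocol 12.1 and 12.5) and, in an unblinded study already under way, would invite the charge of a data-driven change.
- **That percent change needs a baseline floor, such as 3 points.** No such threshold has a source in the documents, and it would create a selected subset.

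**Conclusion.** The point holds as a minor gap in the analysis plan. Percent change in PP-NRS has an unprotected denominator, there is no rule for a zero baseline, and the one by-visit display uses the two statistics most sensitive to a low baseline. One patient worsening from 1 to 3 would move the mean by 12.5 points (n=20) or 10.4 points (n=24), with the others assumed at -50%. How often this would happen cannot be settled from the documents: a baseline below 1 in at least one patient has a chance of about 2-3% to 27-31% under the two assumed distributions, before requiring that the patient worsens. The primary efficacy result is untouched, and the Week 26 median and absolute change already planned would be barely affected.

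**What to change.** Change SAP 4.7.3 only, before database lock:

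1. Plot absolute change from baseline in the 7-day average PP-NRS by visit, in place of or beside the percent-change plot, and summarize it at each scheduled visit.
2. Lead the percent-change summary with the median, keeping the mean and SD as supporting figures.
3. State that patients with a zero baseline are excluded from percent change only, stay in the measured-value and absolute-change summaries, and are reported by number.

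The protocol endpoint stays as written, and no baseline threshold is added. Absolute change is already derived for Week 26, so the cost is one added or replaced figure, a by-visit table and a sentence of rule. The drawback is that the median is a less familiar lead statistic for percent change.
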